5.3 Subject Population

The research population to be studied will include male or female military healthcare beneficiary of any race or ethnicity, aged 18 years or older, who is being treated for a traumatic wound at WRNMMC. With a target enrollment of 20 evaluable subjects, this investigation will include individuals treated for traumatic wounds at WRNMMC with full-thickness wounds, with loss of the dermis extending to deeper tissue layers and disrupting dermal blood vessels, and deep partial-thickness wounds, with injury limited to the epidermis and superficial dermis with no damage to the dermal blood vessels that were successfully treated with INTEGRA™ MBWM. Successful INTEGRA™ MBWM engrafting is defined as the presence of a contiguous vascularized granulation layer.

It is planned to enroll a sufficient number of subjects at WRNMMC in order to ensure a total number of 20 evaluable subjects. Therefore, up to 30 subjects will be consented and enrolled then screened to achieve a maximum of 20 evaluable subjects. Subjects who do not receive treatment with the assigned study device (ReCell) will be considered non-evaluable and therefore a screen failure for study participation.

WRNMMC will be the coordinating center for this clinical trial and will be the only site to enroll subjects for participation. The University of Pittsburgh, UPMC Center for Innovation in Restorative Medicine (CIRM), under the direction of Dr. [name] will be the Sponsor of the IDE and will also function as the Data Coordinating Center (DCC) accountable for maintaining oversight of all data management activities to ensure quality and integrity with accurate reporting, interpretation and verification, and will ensure systems and procedures are in place for the protection and safeguarding of the confidentiality of all data records.

It is anticipated the availability of the study population will be derived from the investigators' clinical practices, individuals evaluated and/or referred by healthcare providers aware of the study within the WRNMMC Orthopaedic Surgery, Plastic Surgery and General Surgery Clinics. Additionally, study participants will be recruited by use of a posting on the research registry at www.clinicaltrials.gov. Those interested

in study participation will be instructed to contact a study team member. This study will not use any advertisements, flyers or brochures.

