Following discussion of the protocol, including a thorough explanation of the experimental procedures, written informed consent and Health Insurance Portability and Accountability Act (HIPAA) authorization will be obtained from all subjects prior to performing any study-related tests or procedures. The subject will then be enrolled into the study and assigned a unique 3-digit study ID number that will be used throughout the study to code all protected health information (PHI). The investigator will maintain a Subject Enrollment Log for all participants consented and enrolled into the study. The master Subject Enrollment Log will be kept in the study regulatory files in a locked file cabinet located in the Orthopaedic Surgery Clinic at WRNMMC.

After the subject has been consented, he/she will undergo thorough screening procedures to assess eligibility to participate in the study. The specific screening procedures are outlined below.

Screening Pre-Treatment/Baseline Assessments:

Screening procedures will be performed by an investigator (PI and/or AI) up to 30 days prior to receiving treatment with the investigational device.

A member of the study team will obtain a medical history including current medication use and allergies derived from both subject reporting and information obtained from a review of their medical record with a focus on pre-existing conditions that may interfere with wound healing. The surgical report from the INTEGRA™ MBWM treatment procedure will be included as part of the medical history and relevant data will be captured on the Baseline Medical History eCRF. Demographic information (date of birth, gender, race/ethnicity) will be recorded on the eCRF.

As part of the inclusion eligibility criteria, the subject will undergo a physical examination to include obtainment of the subject's height, weight, temperature and vital signs (heart rate, respiratory rate and blood pressure). Findings will be recorded on the eCRF. Any conditions or symptoms reported after the subject receives investigational product will be recorded as an adverse event (AE) on the AE eCRF. This includes new events after study device administration, conditions that become more severe or increase in frequency, any disease-related signs or symptoms present at the Screening Pre-Treatment visit that have worsened in severity or frequency, as well as any event or finding that the Investigator feels is clinically significant.

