An evaluation of the traumatic wound area treated with INTEGRA™ MBWM will be made and recorded on the eCRF. The total wound area will be measured. The wound area will be inspected to ensure all areas of the study wound has fully engrafted as indicated by the formation of a viable granulation layer as this will allow for grafting. Both of these findings will be recorded on the eCRF.

A baseline assessment for heterotopic ossification will be established using radiographic imaging. Anterior/posterior and lateral films of the wound area targeted for treatment will be obtained. If the subject's medical record contains an x-ray taken of the wound area targeted for treatment within 30 days prior to enrollment indicating the presence or absence of heterotopic ossification, these radiograph images (x-rays) may be used to avoid unnecessary exposure to radiation.

A baseline assessment for pain and pruritus at the traumatic wound site will be obtained for comparison after receiving study treatment with ReCell. Subjects will be asked to rate their pain using a 0-10 point verbal numerical rating scale where "0" equals no pain and "10" equals worst pain possible. Additionally, the subject will be questioned if experiencing pruritus at the targeted wound site. If so, he/she will be asked to rate the intensity using the following options: mild, moderate and severe. Responses from both assessments will be recorded on the eCRF.

A blood sample (15 mls) will be drawn for hematological analysis including a complete blood count (CBC) with differential panel, coagulation studies to include prothrombin time (PT) and international normalized ratio (INR) and comprehensive metabolic panel (CMP). Results will be reviewed by a physician investigator and documented on the eCRF.

The total time of participant commitment for this portion of the screening pre-treatment baseline assessments including the consenting process will take approximately 1.5 to 2 hours.

Each subject must meet all inclusion and no exclusion criteria in order to qualify for receiving treatment using the ReCell device. The PI or designee will make the final determination of subject eligibility. Subjects who sign the informed consent/HIPAA authorization document, but do not meet eligibility criteria will be defined as a screen failure. The investigator will maintain a screening log that documents the subject ID number and reason(s) for screen failure.

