Subjects will be anesthetized and the wound will be prepared according to hospital standard of care practices. It is anticipated that the total surgical time will be up to 3 hours. The operative procedure will be performed by the PI and/or the Co-PI in the operating room at WRNMMC. The INTEGRA™ MBWM treated wound will be sectioned into two **similarly sized** study regions up to 320cm² each, the upper limit of application area for one ReCell kit. The surgeon will label these two regions “A” and “B” with a surgical pen. A pre-generated randomization envelope will then be opened to determine which area will be the control area and which area will be treated with ReCell. Any wound area outside the study regions will be treated according to standard of care.

In this study, serial histology assessments of the wound site will be made. Baseline punch biopsies of 3 mm diameter tissue samples from the INTEGRA™ MBWM treated wound site and adjacent normal skin will be obtained in the operating room prior to start of the surgical procedure. This baseline histological analysis will examine the vasculogenesis and cytology of the regenerate before ReCell treatment. The biopsy procedure will be recorded in the eCRF.

A digital photograph will be taken of the control and ReCell sites (“A” region and “B” region) and noted on the eCRF. Next, the wound bed will be gently scrubbed and “prepared” then the thin silicone layer is removed, the wound bed will be prepped and prepared again for receipt of proposed STSG or STSG in conjunction with ReCell regenerative skin treatment system.

Harvesting of autograft will be the same thickness for both control and investigational site; at a depth of 0.012 inch to 0.016 inch which is alignment with standard of care practice. Donor tissue for the STSG for the ReCell treatment area may be harvested from the same area as for the control STSG or separate area. To assess healing of the donor sites for ReCell, the site has to be at a discrete location, but can be collocated, i.e. same thigh, but different area.

A digital photograph will be taken of donor sites following tissue removal and will be noted in the eCRF. These and all subsequent photographs at each study visit will be taken in ambient light, with a consistent background and distance between camera and subject.

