For this 2 x 7 mixed design (i.e., two treatment groups x 7 waves of measurements) with a continuous level outcome, a two-way (completely within) repeated measures ANOVA will be performed with the overarching objective being the test of significance for the two-way treatment x time interaction (using $\alpha = .05$). If the two-way interaction is significant, simple effects analysis will be performed so as to assess at which time point significant differences for the treatment variable are obtained. Moreover, if the first order interaction is significant, trend analysis will be conducted in an effort to uncover any nonlinear patterns across time (up to polynomial $t - 1$, where $t = \text{time}$). Graphic displays will be provided so as to illuminate the nature of the findings and the between treatment trajectories.

All assumptions will be examined, including sphericity and homogeneity of variance/covariance matrices and any data anomalies (e.g., outliers) will be examined and treated accordingly. It should be kept in mind that given the small sample size ($n = 20$), there may still be substantive effects despite non-significant results, hence univariate and multivariate effect sizes will be reviewed (e.g., partial η^2).

There are many techniques beyond a mixed ANOVA approach that can more dynamically model the longitudinal nature of this design, such as multilevel modeling, generalized estimating equations, and/or latent growth curve modeling. However, those techniques will need to be deferred until a larger sample size is obtained. All analysis will be conducted using SPSS 21.0 or Stata 11.0.

Analysis Sets of ReCell Device Treatment vs. Control Comparison:

Safety Analysis Set:

The safety analysis population will include all enrolled subjects. Data will be analyzed based on treatment received. The number and percentage of subject who discontinued the study due to adverse event will be provided. Also, descriptive statistics, as

appropriate, will be provided for the following, by treatment:

- Delayed healing/non-healing of wound and donor site
- Graft loss
- Heterotopic ossification
- Infection
- Scar contracture
- Durability (i.e. abrasions/injuries at graft site due to graft fragility)
- Allergic response to trypsin
- Subject Complaint (pain and itching)
- Vital Signs
- Blood chemistries and hematology

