Identification of Adverse Events (AEs), Adverse Device Effects (ADEs) An adverse event is defined as any new medical problem or exacerbation of an existing problem, experienced by a subject while enrolled in the study after receiving investigational product, whether or not it is considered related to the investigational device by the Investigator.

Treatment-Related Adverse Event

A treatment-related adverse event is an adverse event that is judged to be related to the investigational device, study therapy and study-related procedures.

Unexpected Adverse Event

An unexpected adverse event is any adverse effect which the frequency, specificity or severity is not consistent with the risk information described in the investigational plan.

Anticipated (Expected) Adverse Event

Potential adverse event that a subject may experience following the use of the ReCell device as described in this section above and using the potential risks listed in the above tables.

Definitions of Specific Major Treatment –Related Adverse Events:

Infection: The presence of infection for the ReCell treated areas and control site will be evaluated at each post-treatment visit. Infection will be evaluated in accordance with the Center for Disease Control (CDC) guidelines for nosocomial infections using standard clinical measures such as visual examination of the treatment sites for delayed healing, redness, inflammation and surrounding cellulitis. In the presence of symptoms (i.e., purulent exudate, changes in wound appearance such as hyperemia, and erythema in the uninjured skin surrounding the wound), infection will be confirmed using microbiological testing procedures and treatments initiated according to the institutions' infection management protocols, which will be recorded on the eCRF and Adverse Event form. Infection will be managed according to the standard protocols of the clinical site. For example, treatment of infection will involve the daily cleaning and dressing of wound sites until such time that the infection is clear. Treatment with broad spectrum antibiotics until microbiology sensitivities return from the testing laboratory is recommended. Upon return of sensitivities, antibiotic therapy may either continue as is, or be changed at the discretion of the investigator. All treatment regimens applied in the management of infection will be recorded on the eCRF.

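### The safety set counts everyone who consented, so up to 10 of 30 members may be untreated, and the screen-failure label reaches subjects already randomised

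*Combined protocol and SAP*

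**What the plan says.** Section 5.7.3 (Safety Analysis Set) states: "The safety analysis population will include all enrolled subjects. Data will be analyzed based on treatment received". It asks for the number and percentage of subjects who discontinued because of an adverse event, and for descriptive statistics by treatment on the listed safety endpoints. It then asks for adverse event tables giving the percent of subjects affected. No denominator is stated for any of these.

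Enrolment comes early. Section 5.3 says that "up to 30 subjects will be consented and enrolled then screened to achieve a maximum of 20 evaluable subjects". Section 5.5.4 has the same order: after consent, "The subject will then be enrolled into the study and assigned a unique 3-digit study ID number", and then "After the subject has been consented, he/she will undergo thorough screening procedures to assess eligibility to participate in the study".

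Section 6.2 defines an adverse event as a new or worsened problem "experienced by a subject while enrolled in the study after receiving investigational product". Elsewhere in 6.2 safety is monitored from enrolment, and the schedule of assessments (adverse events row and footnote o) also collects adverse events from enrolment.

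Screen failure has two definitions. Section 5.3: "Subjects who do not receive treatment with the assigned study device (ReCell) will be considered non-evaluable and therefore a screen failure for study participation". Section 5.5.4: "Subjects who sign the informed consent/HIPAA authorization document, but do not meet eligibility criteria will be defined as a screen failure". Randomisation takes place in the operating room (5.5.4, Surgical Procedure and Methods): once the surgeon has labelled the two regions, "A pre-generated randomization envelope will then be opened to determine which area will be the control area". Donor harvest and preparation of the ReCell suspension are described after that step.

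**The concern.** Safety and tolerability are the primary outcome (5.7.1), and 5.7.2 says that the results may be used to refine a pivotal trial. A safety percentage should be taken over people who were exposed to the risk. A set defined at consent also holds people who were screened out and never went to surgery. Under the 6.2 definition they cannot have an event, so their inclusion can only lower the percentage.

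The second issue concerns the other end of the process. In a device feasibility study, whether the product can be prepared and applied is itself a result. If a subject is randomised and the suspension then cannot be made or applied, section 5.3 reclassifies that subject as non-evaluable and a screen failure. Section 5.5.4 bars replacement only of withdrawn subjects who received study treatment, so this subject may be replaced. The 20 evaluable subjects would then consist only of those in whom the procedure succeeded, by an exclusion made after randomisation.

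**Working it through.** **Inputs.** Enrolled: up to 30 (5.3). Evaluable: at most 20, all given ReCell (5.3). Untreated members of the safety set: up to 30 − 20 = 10. The documents give no expected screen-failure rate, so the enrolled number n is taken as 22, 25 and 30 (assumed, up to the stated maximum). The plan computes no figure on this point that could be reproduced; its power table concerns a different question.

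**Step 1: shrinkage of per-subject percentages.** If x treated subjects have an event and untreated subjects cannot have one, the reported rate is x/n and the rate among treated subjects is x/20. The ratio is 20/n.

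| Enrolled n | Factor 20/n | 1 event | 2 events | 4 events | Exact 95% upper limit, 0 events |
|---|---|---|---|---|---|
| 20 (treated only) | 1.00 | 5.0% | 10.0% | 20.0% | 16.8% |
| 22 | 0.91 | 4.5% | 9.1% | 18.2% | 15.4% |
| 25 | 0.80 | 4.0% | 8.0% | 16.0% | 13.7% |
| 30 | 0.67 | 3.3% | 6.7% | 13.3% | 11.6% |

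The upper limit for zero events is 1 − 0.025^(1/n), two-sided Clopper-Pearson. Section 5.7.3 plans intervals only around means or mean differences, so these limits show what a reader would infer from the counts; they are not planned output.

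**Step 2: which tables are exposed.** The adverse event tables and the discontinuations due to adverse events are per subject, with no denominator but the defined set. The endpoint tables are by treatment received. A person who was never treated has no ReCell or control region, so those tables can be read as having 20 per column. One total graft loss could therefore appear as 1/20 = 5.0% in the endpoint table and 1/30 = 3.3% in the adverse event table. Section 6.2 places total graft loss at 5% to under 10%; the first figure lies in that band and the second below it.

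**Step 3: subjects randomised but not given ReCell.** The order in 5.5.4 is anaesthesia, labelling of regions, envelope, harvest, preparation, application. Section 5.3 makes no exception for subjects past the envelope, whereas the 5.5.4 definition of screen failure covers ineligibility only. For illustration (assumed counts, none given), let m randomised subjects not receive ReCell and be replaced until 20 are treated:

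- m = 1: 1/21 = 4.8% (exact 95% CI 0.1% to 23.8%)
- m = 2: 2/22 = 9.1% (1.1% to 29.2%)
- m = 3: 3/23 = 13.0% (2.8% to 33.6%)

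Among the 20 evaluable subjects the count is zero by construction. Section 5.7.3 summarises biopsy size, wound size and application details, but no failure proportion over those randomised.

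**Step 4: harm before application.** A subject who was anaesthetised, biopsied and harvested but never given the suspension is in the all-enrolled safety set. Yet harm to that subject falls outside the 6.2 adverse event definition, while the schedule would collect it.

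**The case against.** The strongest reply is that the second sentence of the safety definition, analysis by treatment received, already repairs the first. All listed primary safety items are summarised by treatment, and untreated people drop out of such tables. A reader might infer from the all-enrolled wording that every safety rate will come out one third too low. The documents do not support that. Only the per-subject adverse event and discontinuation percentages are exposed, one third is the maximum, and within-patient ratios of ReCell to control rates do not change. What remains is that the literal rule gives a wrong denominator for those per-subject tables and leaves two candidates for the primary outcome.

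It can also be said that untreated subjects could contribute events, because the schedule and other parts of 6.2 collect from enrolment. That is fair, and it makes the zero-numerator premise one reading of inconsistent text. The other reading is no better, since it mixes pre-treatment events into a treatment safety rate.

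A reader might further infer that device failures vanish from the record. They do not. A back-up kit is in the operating room. Malfunctions that lead to replacement or an adverse event go to the eCRF. Device and surgical problems are collected at surgery (5.5.5), screen-failure reasons are logged, and all collected data are listed. Nor do most processing risks in 6.2 imply that ReCell was not given: low cell viability still yields a suspension, and a spare nozzle is supplied. Inability to separate the biopsy is the plausible route. What is missing is a summary rate over randomised subjects.

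Finally, the Effectiveness Analysis Set has no membership rule, so the exclusion of these subjects from it is inferred from the non-evaluable label in 5.3 and is not stated.

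**Conclusion.** The concern holds in a limited form. The stated safety set is the wrong denominator for per-subject adverse event and discontinuation percentages. If it is used as written together with the 6.2 definition, they are too low by 20/n: 0.91 to 0.67 for 22 to 30 enrolled, with 30 the protocol maximum. The size depends on how many enrolled subjects go untreated, which the documents do not predict. The direction is always favourable to the device.

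The screen-failure label in 5.3 conflicts with 5.5.4, reaches subjects already randomised, allows their replacement, and leaves preparation or application failure without a planned rate. The individual cases stay traceable, so the loss is one of summary and not of data.

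The study is small and descriptive, and treated-only rates can be recomputed from the listings. It still merits correction before data are reviewed, because choosing between denominators afterwards would be a post hoc decision on the primary outcome.

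**What to change.** In 5.7.3, define the safety set as all subjects in whom any study operative procedure (anaesthesia, baseline biopsy or harvest) was begun, with region-level tables by the treatment actually applied. Starting at envelope opening would be too late, since anaesthesia and wound preparation come first and the baseline biopsies are taken before the graft surgery starts. Show subjects who leave earlier in the disposition table only.

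In 5.3, limit screen failure to exits before randomisation and reconcile it with 5.5.4. Keep a randomised set, and report the proportion in whom ReCell could not be prepared or applied, with an exact 95% CI. Give the Effectiveness Analysis Set a membership rule. State the denominator of every table. Reconcile the adverse event start point in the 6.2 definition with the from-enrolment statements in 6.2 and the schedule of assessments.

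The cost is a few sentences in 5.3, 5.5.4, 5.7.3 and 6.2 and one added summary, with no extra patients or data. Reported event rates may look slightly less favourable.
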